7.3 Analysis of Anthropometric, Metabolic, Fitness and QOL Measurements

All of the anthropometric, metabolic, fitness and QOL measurements are continuous variables. After assessing for normality, changes from baseline will be made using a paired t-test if the distribution is normal or by the Wilcoxon signed-rank test if the distribution is non-normal.

8. SAFETY MONITORING AND REPORTING

8.1 Adverse Events and Serious Adverse Events:

Adverse events (AE) and serious adverse events (SAE) as a result of participating in the study are not expected because EXERT-BC is an observational study, including quality of life questionnaires.

From the time the subject signs the informed consent form through the exercise program completion visit, data will be collected for all AEs and SAEs recorded in the subject's medical record and adverse events case report form for summary reporting of the study's objective.

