3 PROTOCOL SYNOPSIS

3.1 Purpose:

This protocol seeks to analyze patient outcomes of the standard of care, monitored group exercise regimen of high-load resistance training and functional exercises with compound movements under close supervision on women who have been treated for breast cancer.

Primary Objective

- 1 Determine safety and feasibility measured by exercise compliance.

Exploratory Objectives

- 1 Determine changes in functional mobility testing changes at baseline, throughout, post-exercise assessment and 1 year after exercise assessment.
- 2 Determine quality of life at baseline, throughout, and post- exercise assessment
- 3 Determine changes in strength and load lifted at baseline, throughout, post-exercise assessment, and 1 year after exercise assessment.
- 4 Determine changes in resting metabolic rate at baseline, throughout, post- exercise assessment, and 1 year after exercise assessment.
- 5 Determine changes in body composition at baseline, throughout, post- exercise assessment and 1 year after exercise assessment, including body mass, fat mass, fat-free mass, % fat, and % fat-free mass.

Hypotheses

In this study, we hypothesize that an observed exercise regimen utilizing high-load resistance training initiated during or after cancer treatment is safe and feasible in women and may improve functional mobility, body composition, and resting metabolic rate.

3.2 Background and Significance:

Obesity is a risk factor for both breast cancer and disease recurrence after treatment.¹ Furthermore, weight gain during and after treatment for breast cancer is associated with a higher risk of recurrence, distant metastases, and death.² Yet, most women gain significant weight during and after breast cancer treatment, potentially compromising outcomes.

Contrary to these findings, activity levels have been repeatedly associated with a lower risk of breast cancer incidence, improved outcomes after breast cancer treatment, and improved breast cancer-specific and overall survival.³ The majority of breast cancer survivors do not meet adequate daily activity level recommendations, potentially compounding issues with weight gain during and after breast cancer treatment.⁴ As a result, attempts are underway to both quantify and increase activity levels during treatment and survivorship.⁵ Furthermore, and based on these findings, several areas of

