Studies in non-cancer patients reveal that resistance training routines that expose muscle tissue to extensive mechanical tension with subsequent muscle damage and metabolic stress promote training-induced muscle growth.²⁴ Additionally, more intense and heavier weight lifting regimens have been consistently shown to improve several factors associated with health, including: 1) Improved strength and fitness and decreased risk of injury, 2) Increased muscle mass and corresponding decrease in inflammation,²⁵ 3) Enhanced insulin sensitivity, elevated resting metabolic rate, and decreased risk of diabetes,⁴ 4) Improved mobility and overall health,²⁶ and 5) Increased bone mineral density.²⁷ Furthermore, resting metabolic rate, which comprises the majority of daily total energy expenditure, is proportional to muscle mass.²⁸ Additionally, excess postexercise oxygen consumption (EPOC), or the continued enhanced metabolic effect after the completion of exercise, is enhanced via strenuous resistance training compared with aerobic training alone.²⁹

While weight training has clear advantages over aerobic training for improving body composition and several measurable metabolic variables, there have been barriers to its implementation in exercise regimens for the breast cancer patient, including concerns of safety and lymphedema risk.³⁰ However, as stated above, these risks have been largely disproved by the current available research.³¹ Adverse effects (AEs) reported in prior exercise studies include typical self-limiting musculoskeletal issues, including muscle strains, joint and back pain, shin splints, and tendinitis.³² Overall, AEs are minimal. Furthermore, an observed environment with supervision by trained exercise personnel can further reduce the risk of injury,^{33,34} as can adaption of a workout regimen that accounts for individuals' functional movement abilities, mobility, and function.³⁵

3.3 Rationale:

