6. PATIENT ASSESSMENTS

Table 1: Participant Assessments

Assessment	Screening	Baseline Assessments (Prior to Program)	During Exercise Program	At Exercise Program Completion	1 Year After Exercise Program Completion
Consent	X				X ^f
History/Physical	X				
Weight, height, and BMI	X			X	X
Body Composition Assessment ^a		X		X	X
Resting Metabolic Rate Assessment		X		X	X

QOL and Exercise Forms ^b		X		X	X
Strength Assessment ^{c,d}		X	X	X	X
Mobility Assessment ^c		X		X	X
Compliance ^e			X		

- a To calculate lean and fat mass and percentages, and total energy expenditure (kcal/day) SOC
- b EQ-5D-5L, and Leisure-Time Exercise Questionnaire SOC
- c Functional Mobility Survey and Y-balance test, includes grip strength SOC
- d Will also occur periodically throughout program to adjust exercise regimen SOC
- e Attendance collected at each workout
- f Verbally reconsent to use SOC data for research purposes

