7. STATISTICAL METHODS AND DATA ANALYSIS

7.1. Analysis of Safety

Safety will be continually assessed during each workout regimen by the exercise physiologist, and adjustments will be made to exercise performance during the workout to increase safety as per standard of care.

The AEs will be reviewed and assessed by the PI and reported per AHN IRB reporting requirements. Accidental disclosure of confidentiality is the only adverse event that would occur.

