Subject names or identifiers will not be used in reports, presentations at scientific meetings, or publications in scientific journals.

Data Collection:

The following data will be stored in the secure database:

- Age
- Diagnosis
- Weight, height, and BMI
- Comorbid medical conditions
- Surgical procedure for breast cancer or orthopedic procedures
- Type of hormonal therapy
- Body composition at start/completion (body fat percentage, % fat-free mass, fat mass, fat-free mass, body mass)
- Resting metabolic rate at start/completion
- Exercise details (specific exercise, repetitions, weight, load lifted)
- FMS and Y-balance test
- Grip strength at start/completion
- QOL forms (EQ-5D-5L)
- Godin Leisure-Time Exercise Questionnaire
- Adherence rates (percentage classes)
- Assessments that are SOC

10.5 Protocol Amendments:

All protocol amendments must be initiated by the Principal Investigator and approved by the IRB prior to implementation. IRB approval is not required for protocol changes that occur to protect the safety of a subject from an immediate hazard. However, the Principal Investigator must inform the IRB and all other applicable regulatory agencies of such action immediately.

10.6 Records Retention:

The Principal Investigator will maintain study-related records for the longer of a period of at least six years after study completion, or per AHN policy, whichever is more strict.

APPENDICES

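### Safety is part of the primary objective, but no adverse-event question is scheduled and nothing ties class observation to the AE form, so minor injuries may go unrecorded

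*Combined protocol and SAP*

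**What the plan says.** - **Objective (3.1).** There is one primary objective: "Determine safety and feasibility measured by exercise compliance". The hypothesis in the same section includes that the regimen is safe.
- **Schedule (section 6, Table 1).** No row covers adverse events, injuries or symptoms. During the program the marked rows are strength and compliance; the footnote to compliance reads "Attendance collected at each workout". History and physical examination is marked at screening only.
- **Sources and window (8.1).** The section states that "data will be collected for all AEs and SAEs recorded in the subject's medical record and adverse events case report form". The window runs "From the time the subject signs the informed consent form through the exercise program completion visit".
- **In-class observation (7.1).** The exercise physiologist assesses safety throughout each workout, and "adjustments will be made to exercise performance during the workout to increase safety as per standard of care". The investigator reviews adverse events and reports them to the ethics board's requirements.
- **Session log (5.3).** Load, repetitions, sets and notes are recorded; the stated use is the volume-load calculation.
- **Data list (10.4).** The list opened by "The following data will be stored in the secure database" contains no adverse-event or injury item.
- **What is anticipated.** Section 3.2 says that earlier exercise studies reported "typical self-limiting musculoskeletal issues, including muscle strains, joint and back pain, shin splints, and tendinitis". Section 8.1 says adverse events from taking part are not anticipated, and 7.1 names a breach of confidentiality as the sole adverse event foreseen.

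**The concern.** The question is how events are found, before any question of how they are summarised. The harms described in section 3.2 are ones that supervising staff can manage on the spot by changing an exercise. Such an event need not produce a clinic note, and it reaches the AE form only if somebody decides to put it there. The plan names nobody to make that decision, and two of its own statements suggest to staff that there will be nothing to log.

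A low count would then be read as support for the hypothesis that high-load training is safe, when part of it could reflect that nobody asked. Women who stop because of pain are a particular worry, since the end of the collection window is tied to a visit they may not attend.

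**Working it through.** The documents give no adverse-event rate, safety threshold or safety sample size, so there is no planned figure to reproduce. The 0.56 bound in section 7.2 concerns attendance only. The check is to follow an event through the plan.

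**1. Opportunities to observe.** Section 5.3 gives three supervised classes a week for 12 weeks: 3 × 12 = 36 classes per woman. The staff contact needed for systematic capture already exists.

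**2. A strain noticed in class.** The physiologist adjusts the exercise, as 7.1 directs. Where is the event written down?
- *Table 1:* there is no row for it.
- *Session log (5.3):* perhaps in the notes, but no injury field is named and no step carries a note to the AE form.
- *Medical record (8.1):* only if someone charts it or the woman raises it with a clinician.
- *AE form (8.1):* only if someone classes it as an adverse event, against the statement in 7.1 that a confidentiality breach is the only one foreseen.
- *Database (10.4):* no listed item receives it.

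**3. Pain that starts between classes.** No class or visit includes a question about new pain or injury since the last contact. Unless the woman volunteers it, none of the steps above begins.

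**4. A woman who stops early.** Collection in 8.1 ends at the program completion visit, and no date is given for someone who never has that visit. Section 7.2 puts the proportion who quit the regimen at 20%, so this gap would concern about 0.20 × 40 = 8 women; that is the number exposed to the gap, not a number of missed events. Section 6.5 has the investigator note the reason for leaving the study. Section 6.5.2 says that there is no follow-up after withdrawal and also that data collection will be attempted after the exercise program is discontinued. It does not say whether that includes adverse events.

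**5. Direction.** If a proportion p of women have an event and a fraction c of those women have it recorded, the recorded proportion is p × c. Leaving aside false reports, c is at most 1, so incomplete capture can only lower the reported rate.

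**6. Size.** Neither p nor c appears in the documents, so p × c cannot be evaluated.

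**The case against.** The plan is not blind to harm. The AE form is a study instrument, separate from the chart. Qualified staff watch every class, loads and notes are logged, and the investigator reviews adverse events. Reasons for leaving the study must be recorded. Pain also surfaces elsewhere: the EQ-5D-5L has a pain item (Appendix II) and the movement screen scores zero when a movement hurts (Appendix V), both at baseline, completion and one year. The statements in 7.1 and 8.1 can also be read as referring to the research activity alone, with the exercise itself treated as standard care.

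Much of this stands, and it rules out several stronger readings that a reader might infer:
- *That capture rests on the medical record alone.* Section 8.1 names the form as well.
- *That only attendance is collected at each class.* Section 5.3 shows that loads and notes are logged too.
- *That the protocol expects these injuries.* Section 3.2 describes earlier studies; 7.1 and 8.1 say the opposite for this one.
- *That collection must run to one year.* Ending with the supervised program is a defensible exposure window, and use of the one-year data falls under separate reconsent (Table 1 and section 10.2).

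What does not stand is the step from observing to counting. No text links the physiologist's observation or the notes to the form. The pain items are taken at widely spaced assessments and do not identify events. If 7.1 and 8.1 mean research-related harm only, they do not say so, and that scope would leave the safety of the regimen, which is what the hypothesis concerns, without a stated measure.

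**Conclusion.** The concern holds as a risk of under-recording. Safety is part of the primary objective, no adverse-event assessment is scheduled, and the route from what staff see to what is counted is not defined. The statements in 7.1 and 8.1 conflict with section 3.2 and give staff little reason to log a minor injury. Any resulting loss runs toward the hypothesised conclusion.

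A reader might go further and say that injuries will be under-counted by some stated amount, or that the reported interval will exclude the true rate. The documents do not support that. Any such figure needs an assumed injury rate and an assumed capture fraction, and the result turns on both choices. The conclusion here rests on one judgement: that self-limiting injuries are less likely to reach a chart or form when nobody is assigned to ask about them.

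**What to change.** 1. Add an adverse-events row to Table 1, marked at each class and at program completion.
2. At each class, have the staff member who logs attendance record two yes/no items: new pain or injury since the last class, and any exercise modified or stopped because of symptoms. Each yes is transferred to the AE form. Name the role responsible for completing the form.
3. In 8.1, fix the end of collection: the completion visit or, for women who stop early, 12 weeks from the first session. Reconcile this with the two statements on follow-up in 6.5.2.
4. Add adverse events to the data list in 10.4.
5. Reconcile the statements in 7.1 and 8.1 with section 3.2. If they are meant to cover research-related harm only, say so and keep exercise-related events within the safety objective.

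The cost is two tick-boxes per session on a log already kept, an added database item, and some effort to reach women who stop early. The reported adverse-event rate may look less favourable, and the sponsor should accept that in advance. Injuries not asked about at the time are hard to recover later, so the change is best made before further classes are run.

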9. QUALITY CONTROL AND QUALITY ASSURANCE

9.1 Monitoring:

This clinical research study will be monitored continuously by the PI for study conduct and data to ensure that:

Risk/benefit ratio is not altered to the detriment of the subjects;

Over-accrual does not occur;

Under-accrual is addressed with appropriate amendments or actions;

Data are being appropriately collected in a reasonably timely manner.

10. ADMINISTRATIVE AND ETHICAL CONSIDERATIONS

10.1 Regulatory and Ethical Compliance:

This protocol was designed and will be conducted and reported in accordance with the International Conference on Harmonization (ICH) Harmonized Tripartite Guidelines for Good Clinical Practice, the Declaration of Helsinki, and applicable federal, state, and local regulations.

10.2 Informed Consent:

The informed consent form is written in a manner that is understandable to the subject population. Prior to its use, the informed consent form must be approved by the IRB. The Principal Investigator or authorized key personnel will discuss with the potential subject the purpose of the research, methods, potential risks and benefits, subject concerns, and other study-related matters. This discussion will occur in a location that ensures subject privacy and in a manner that minimizes the possibility of coercion.

Appropriate accommodations will be made available for potential subjects who cannot read or understand English or are visually impaired that are first approved by the IRB. Potential subjects will have the opportunity to contact the Principal investigator or authorized key personnel with questions and will be given as much time as needed to make an informed decision about participation in the study.

Before conducting any study-specific procedures, the Principal Investigator or authorized key personnel must obtain written informed consent from the subject or a legally acceptable representative. The original informed consent form will be stored with the subject's study records, and a copy of the informed consent form will be provided to the subject. The Principal Investigator is responsible for asking the subject whether the subject wishes to notify his/her primary care physician about participation in the study. If the subject agrees to such notification, the Principal Investigator will inform the subject's primary care physician about the subject's participation in the clinical study.

Reconsenting of the subjects will be conducted at the time of SOC assessments. PI and/or study staff will inform the subjects that their 1 year follow up assessment data will also be used for research purposes. A note of this consenting with the subjects will be placed in the research record and EPIC. If subject does not consent, their follow up assessment data will not be used for research.

10.3 Study Documentation:

Study documentation includes but is not limited to source documents, case report forms (CRFs), monitoring logs, appointment schedules, study team correspondence with sponsors or regulatory bodies/committees, and regulatory documents that can be found in the AHN electronic "regulatory binder."

Source documents are original records that contain source data, which is all information in original records of clinical findings, observations, or other activities in a clinical trial necessary for the reconstruction and evaluation of the trial. Source documents include but are not limited to hospital records, clinical and office charts, laboratory notes, memoranda, evaluation checklists, and subject files. When possible, the original record should be retained as the source document. However, a photocopy is acceptable provided that it is a clear, legible, and an exact duplication of the original document.

10.4 Privacy, Confidentiality, and Data Storage:

The Principal Investigator will ensure that subject privacy and confidentiality of the subject's data will be maintained.

To protect privacy, every reasonable effort will be made to prevent undue access to subjects during the course of the study. Prospective participants will be consented in an exam room where it is just the research staff, the patient and her family, if desired. For all future visits, interactions with research staff (study doctor and study

coordinators) regarding research activities will take place in a private exam room. All research related interactions with the participant will be conducted by qualified research staff who are directly involved in the conduct of the research study.

To protect confidentiality, subject files in paper format will be stored in secure cabinets under lock and key accessible only by the research staff. Subjects will be identified only by a unique study number and subject initials. Electronic records of subject data will be maintained using a secure password-protected database. Access to the database will be limited to essential study personnel. Subject data may be stored temporarily on encrypted and password-protected portable memory devices such as flash drives and external hard drives, but only when absolutely necessary. Data stored on portable memory devices will be de-identified. Subject data will be deleted from the portable memory device at the earliest opportunity.

Upon completion of the study, research records will be archived and handled securely.

Subject names or identifiers will not be used in reports, presentations at scientific meetings, or publications in scientific journals.

Data Collection:

The following data will be stored in the secure database:

- Age
- Diagnosis
- Weight, height, and BMI
- Comorbid medical conditions
- Surgical procedure for breast cancer or orthopedic procedures
- Type of hormonal therapy
- Body composition at start/completion (body fat percentage, % fat-free mass, fat mass, fat-free mass, body mass)
- Resting metabolic rate at start/completion
- Exercise details (specific exercise, repetitions, weight, load lifted)
- FMS and Y-balance test
- Grip strength at start/completion
- QOL forms (EQ-5D-5L)
- Godin Leisure-Time Exercise Questionnaire
- Adherence rates (percentage classes)
- Assessments that are SOC

10.5 Protocol Amendments:

All protocol amendments must be initiated by the Principal Investigator and approved by the IRB prior to implementation. IRB approval is not required for protocol changes that occur to protect the safety of a subject from an immediate hazard. However, the Principal Investigator must inform the IRB and all other applicable regulatory agencies of such action immediately.

10.6 Records Retention:

The Principal Investigator will maintain study-related records for the longer of a period of at least six years after study completion, or per AHN policy, whichever is more strict.

APPENDICES

APPENDIX II: Quality of Life – EQ-5D-5L

Under each heading, please check the ONE box that best describes your health TODAY.

MOBILITY

- I have no problems walking
- I have slight problems walking
- I have moderate problems walking
- I have severe problems walking
- I am unable to walk

SELF-CARE

- I have no problems washing or dressing myself
- I have slight problems washing or dressing myself
- I have moderate problems washing or dressing myself
- I have severe problems washing or dressing myself
- I am unable to wash or dress myself

USUAL ACTIVITIES (e.g. work, study, housework, family or leisure activities)

[figure not shown]
- I have no problems doing my usual activities
- I have slight problems doing my usual activities
- I have moderate problems doing my usual activities
- I have severe problems doing my usual activities
- I am unable to do my usual activities

PAIN / DISCOMFORT

- I have no pain or discomfort
- I have slight pain or discomfort
- I have moderate pain or discomfort
- I have severe pain or discomfort
- I have extreme pain or discomfort

ANXIETY / DEPRESSION

- I am not anxious or depressed
- I am slightly anxious or depressed
- I am moderately anxious or depressed
- I am severely anxious or depressed
- I am extremely anxious or depressed

